6.3.3 Criteria for Rechallenge of Amgen Investigational Product After Potential Hepatotoxicity

The decision to rechallenge the subject should be discussed and agreed upon unanimously by the subject, investigator, and Amgen.

If signs or symptoms recur with rechallenge, then Amgen investigational product will be permanently discontinued. Subjects who clearly meet the criteria for permanent discontinuation (as described in [Section 6.3.1](#)) should never be rechallenged.

6.4 Concomitant Therapy

Throughout the study and while the subject is receiving investigational product, investigators may prescribe any concomitant medications or treatments deemed necessary to provide adequate supportive care except **as noted** in [Section 6.5](#). For a subject who prematurely discontinues investigational product, concomitant therapy may be adjusted as needed.

Concomitant therapies are to be collected from enrollment through the end of study. The therapy name, indication, dose, unit, frequency, route, start date, and stop date are to be recorded on each subject's CRF or eDiary.

During the parent study, the subject and investigator are to agree on the medications for the acute treatment of migraine pain and the appropriate dose(s) that the subject may take on an as-needed basis throughout the parent and open-label extension study. Medications for acute treatment of migraine pain include: simple analgesics, combination analgesics, triptans, ergot derivatives, opiates. To avoid confounding the study results, new acute medications for treatment of headache pain should not be introduced and addition of daily medications that fall into the categories of simple analgesics, combination analgesics, triptans, and ergot-derivatives should be avoided, even if the medication is used for indications other than headache.

6.5 Excluded Treatments During Study Period

1. The following medications are excluded **between screening and 4 weeks after last dose of IP**:

- Divalproex sodium, sodium valproate, topiramate, carbamazepine or gabapentin,
- All beta blockers (for example: metoprolol, propranolol, timolol, atenolol, nadolol, nebivolol, pindolol, bisoprolol),
- All tricyclic antidepressants (for example: amitriptyline, nortriptyline, protriptyline),
- Flunarizine or verapamil,
- Venlafaxine, desvenlafaxine, duloxetine or milnacipran,
- Botulinum toxin (injected in the head and/or neck region),
- Lisinopril,
- Candesartan,
- Butterbur, feverfew, magnesium (≥ 600 mg/day), riboflavin (≥ 100 mg/day),
- Clonidine or guanfacine,
- Cyproheptadine,
- Methysergide,
- Pizotifen

2. The following medications are excluded only if used daily throughout the month for migraine prophylaxis **between screening and 4 weeks after last dose of IP**:

- Fluoxetine, fluvoxamine,
- Acetazolamide,
- Picotamide,
- Cyclandelate,
- Ergot-derivatives, steroids, triptans,
- Nicardipine, nifedipine, nimodipine

If the above medications are used daily, but not for migraine prophylaxis, the doses should remain stable **between screening and 4 weeks after last dose of IP**.

3. Investigational drugs, devices or procedures (eg, acupuncture, occipital stimulator, transcranial magnetic stimulation) **between screening and 4 weeks after last dose of IP**.

6.6 Medical Devices

The AMG 334 70 mg/mL SureClick™ AI/pen is a single-use, disposable, handheld mechanical injection device that administers a fixed dose of AMG 334 70 mg/mL into subcutaneous tissue. The AMG 334 **prefilled** AI/pen uses the same components as the

commercially available Enbrel SureClick[®] autoinjector but assembled with a HyFlow syringe.

The AMG 334 PFS is a single-use, disposable, manual injection device that administers a single dose of AMG 334 into subcutaneous tissue. Amgen has developed the AMG 334 PFS presentation using the commercially available sterile 1-mL long glass syringe components procured from Becton Dickinson Pharmaceutical Systems (BD).

In addition, tuberculin syringes will be used in this study. Authorized study staff will use the syringes to pull out investigational product from the vials in the subject's assigned kit and administer the investigational product to the subject.

Subjects participating in the CHU substudy will return the AI/pens or PFS back to the clinic for reconciliation and disposal by the site staff using a plastic box provided by Amgen to the clinical sites. Medical devices that are not considered test articles may be used in the conduct of the study as part of standard of care (except for AI/pen or PFS). These devices, such as alcohol prep pads, are commercially available and are not usually provided or reimbursed by Amgen (except, for example, if required by local regulation). The investigator will be responsible for obtaining supplies of these devices.

Detailed information regarding the medical devices will be provided separately in the IPIM.

6.7 Product Complaints

A product complaint is any written, electronic, or oral communication that alleges deficiencies related to the identity, quality, durability, reliability, safety, effectiveness, or performance of any product(s) or device(s) after it is released to the clinic by Amgen or by distributors, and partners with whom Amgen manufactures the material. This includes any products, devices, **or combination products** provisioned and/or repackaged/modified by Amgen. **Product(s) or device(s) includes IP.** Any product complaint(s) associated with an investigational product or device supplied by Amgen are to be reported according to the instructions provided in the IPIM.

7. STUDY PROCEDURES

7.1 Schedule of Assessments

Refer to the Schedule of Assessments ([Table 1](#)) for an outline of the procedures required at each study visit. Each study visit during the open-label treatment phase and the safety follow-up phase has a window of ± 4 consecutive calendar days. The day 1 visit should occur once a subject has completed all 12-week procedures of the parent

study and within 14 days of the 12-week visit of the parent study. The subject may not enroll in this study on the same day as the week 12 visit of the parent study as the investigator must review the week 12 laboratory data and the central read of the week 12 ECG prior to enrolling the subject in order to assess clinical significance of this data as per exclusion criteria.

All study procedures for a given study visit are to be completed on the same day.

Investigators are responsible for ensuring that all study procedures are performed as specified in the protocol.

Study visits should be conducted without additional non-protocol therapies and subjects should be reminded about the investigational nature of the study drug.

Refer to the applicable supplemental (eg, laboratory) manuals for detailed collection and handling procedures.

Table 1. Schedule of Assessments
General Assessments and Administrative Procedures

	Screening	Day 1 ^a	Wk 4 / M1	Wk 8 / M2	Wk 12 / M3	Wk 16 / M4	Wk 20 / M5	Wk 24 / M6	Wk 28 / M7	Wk 32 / M8	Wk 36 / M9	Wk 40 / M10	Wk 44 / M11	Wk 48 / M12	Wk 52 / M13 / ET	Wk 64/M16 (16 Wks/4M After Last Dose of IP)
Informed Consent	X															
Physical Examination															X	
Weight															X	X
Vital Signs	X ^b		X	X	X	X	X	X	X	X	X	X	X	X	X	X
ECG			X		X			X ^c			X ^d				X	
Concomitant Medications Recording		X	X	X	X	X	X	X	X	X	X	X	X	X	X	X
IP Administration		X	X	X	X	X	X	X	X	X	X	X	X	X		
SAE/AE Recording		X	X	X	X	X	X	X	X	X	X	X	X	X	X	X
Enrollment		X														
Calls to IVR/IWR System ^e	X	X	X	X	X	X	X	X	X	X	X	X	X	X	X	X
Subject Brings eDiary to Site	X	X	X	X	X			X				X			X	

Footnote defined on last page of the table

Table 1. Schedule of Assessments
Laboratory Procedures and Clinical Outcome Assessments

	Screening	Day 1 ^a	Wk 4 / M1	Wk 8 / M2	Wk 12 / M3	Wk 16 / M4	Wk 20 / M5	Wk 24 / M6	Wk 28 / M7	Wk 32 / M8	Wk 36 / M9	Wk 40 / M10	Wk 44 / M11	Wk 48 / M12	Wk 52 / M13 / ET	Wk 64/M16 (16 Wks/4M After Last Dose of IP)	
UDS	Testing as needed throughout study based on investigator's clinical suspicion																
Pregnancy Test-Urine			X	X	X	X	X	X	X	X	X	X	X	X	X		
Pregnancy Test-Serum																X	
Chemistry, Hematology			X		X			X ^c			X ^d				X	X	
Urinalysis																X	
Biomarker Development																X	
PK Sampling								X							X	X	
Anti-AMG 334 Antibodies								X							X	X	
COAs			Daily ^f					Daily ^f				Daily ^f					
Migraine Symptom Interference Items			Daily ^f					Daily ^f				Daily ^f					
PROMIS			Weekly ^f					Weekly ^f				Weekly ^f					
MSQ			X	X	X	X	X	X	X	X	X	X	X	X	X	X	
MIDAS					X			X			X				X		
Novel PRO Substudy: The Migraine Physical Function Impact Diary (MPFID)			Daily ^f					Daily ^f				Daily ^f					
C-SSRS			X	X	X	X	X	X	X	X	X	X	X	X	X	X	

Footnote defined on last page of the table

Table 1. Schedule of Assessments
Clinical Home Use Substudy Assessments

	Screening ^g	Day 1 ^h	Day 28 visit ⁱ	Day 29 Telephone visit	Day 56 visit ^j	Day 57 Telephone visit	Day 85 visit ^k / ET ^l
Informed Consent	X						
Randomization to PFS or AI/pen IP self-administration arm		X					
PFS or AI/pen Instruction ^m	X	X					
Physical Examination		X					
Self-administration IP on-site		X					
Self-administration IP at non-clinic setting				X		X	
Study coordinator IP dispense			X		X		
Study coordinator IP reconcile		X			X		X
Inquiry re: administration of IP				X		X	
Review for ADEs		X	X	X	X	X	X
Review for AEs/SAEs				X		X	
Product Complaints Recording (if applicable)		X	X	X	X	X	X

Footnote defined on last page of the table

-
- ^a Day 1 visit should occur once a subject has completed all 12-week procedures of the parent study and within 14 days of the 12-week visit of the parent study.
- ^b BP should be measured as part of the screening criteria to determine eligibility (no later than at day 1 as long as BP is taken before subject is enrolled via IVR). Note: BP taken at week 12 of the parent study (AMG 334 20120295) should not be used as screening BP.
- ^c Only for subjects who increased IP to 140 mg at week 12, 16, or 20
- ^d Only for subjects who increased IP to 140 mg at week 24 or 28
- ^e Additional steps during IVR/IWR call to accommodate IP dose increase from 70 mg to 140 mg (between week 4 and week 28).
- ^f Collection will start at the end of the applicable scheduled visit and finish at the beginning of the applicable scheduled visit.
- ^g Screening must occur 4 weeks prior to the planned start of the CHU substudy (week 8 or week 36 of the 20130255 study). IVR System will be adjusted to accommodate CHU screening and randomization information as required.
- ^h Day 1 of the CHU is equivalent to either week 12 or week 40 of the 20130255 study.
- ⁱ Day 28 of the CHU is equivalent to either week 16 or week 44 of the 20130255 study.
- ^j Day 56 of the CHU is equivalent to either week 20 or week 48 of the 20130255 study.
- ^k Day 85 of the CHU is equivalent to either week 24 or week 52 of the 20130255 study; subject will receive AMG 334 140mg SC administered by site staff using vial formulation and will continue scheduled procedures and assessments as per 20130255 study.
- ^l ET: If a subject early terminates the CHU substudy, he/she may receive administration of AMG 334 140 mg SC at site as per 20130255 protocol and will continue 20130255 scheduled procedures and assessments as per 20130255 protocol.
- ^m Study coordinator will review PFS or AI/pen training materials (Reference Guide and Instructions for Use) with subject.

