3. EXPERIMENTAL PLAN

3.1 Study Design

This is a multicenter, open-label study designed to assess the long-term safety and efficacy of AMG 334. Subjects who complete the 12-week double-blind treatment phase of the AMG 334 20120295 parent study and meet all AMG 334 20130255 eligibility criteria will be enrolled into the study. Enrollment should occur within 14 days after the parent study's week 12 visit. Subjects who enroll in the AMG 334 20130255 study will end the AMG 334 20120295 study and will not participate in the parent study safety follow-up visit.

All subjects who have not yet enrolled in the study will receive open-label AMG 334 140 mg every month (QM) SC for 13 months. Subjects who are already enrolled in the 20130255 study will increase the open-label dose from 70 mg QM to 140 mg QM at the first available opportunity at either week 4, 8, 12, 16, 20, 24, or 28 visits. Subjects who have already completed the week 28 visit will continue to receive 70 mg QM.

All subjects will receive open-label AMG 334 QM SC for 13 months followed by a 12-week safety follow up visit (16 weeks after the last dose of investigational product [IP]).

Investigational product (ie, AMG 334 70 mg or 140 mg) will be dosed QM, SC.

The overall study design is described by a [study schema](#) at the end of the protocol synopsis section.

The study endpoints are defined in [Section 10.1.1](#).

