10.6 Safety Analyses

For safety endpoints, including laboratory data, vital signs and other non-AE safety data, all enrolled subjects who received at least one dose of investigational product (ie, utilizing the SAS) will be analyzed based on the treatment received in

the 20130255 OLE study. Three treatment groups will be considered, based on planned dosing:

- 70 mg: including all subjects who receive 70 mg for at least 80% of the time exposed
- 140 mg: including all subjects who receive 140 mg for at least 80% of the time exposed
- 70/140 mg mix: including all subjects who receive any one dose <80% of the time exposed

A total AMG 334 group will also be presented in the tables.

For AE safety data two treatment groups will be considered:

- 70 mg
- 140 mg

A total AMG 334 group will also be presented in the tables.

No statistical testing comparing treatment groups will be performed in the safety analyses.

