10.6.2 Laboratory Test Results

Shifts tables of the most extreme post-baseline (after the first IP in 20130255 study) laboratory toxicity based on CTCAE grade relative to 20130255 study baseline will be tabulated by treatment group. Laboratory values and changes from 20130255 study baseline for selected panels may be summarized descriptively by visit and treatment group. In the cases when CTCAE grading scales include numeric ranges in combination with clinical assessment (eg, potassium [hypokalemia]), laboratory test results may be summarized based on standard normal ranges or by CTCAE grade utilizing investigator's input.

Shifts tables of the laboratory toxicity for **absolute neutrophil count (ANC)** based on CTCAE grade relative to baseline will be tabulated by treatment group.

Summary of change from baseline for ANC, alanine aminotransferase (ALT) and aspartate aminotransferase (AST) will also be provided by visit.

Subject incidence of liver function test abnormalities, including AST, ALT, Total Bilirubin (TBL) and Alkaline Phosphatase (ALP), will also be summarized by treatment group.

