10.6.5 Electrocardiogram (ECG)

The ECG measurements from this clinical study were performed as per standard of care for routine safety monitoring, rather than for purposes of assessment of potential QTc effect. Because these evaluations may not necessarily be performed under the rigorous conditions expected to lead to meaningful evaluation of QTc data; neither summaries nor statistical analyses will be provided, and these data would not be expected to be useful for meta-analysis with data from other trials. **A summary of ECG diagnoses will be tabulated.**

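### The 70/140 mg mix column has one more scheduled chemistry/haematology panel per completer than the other dose columns, which tends to raise its worst-grade and liver-abnormality counts

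*Protocol*

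**What the plan says.** **Schedule.** In Protocol Table 1, the row "Chemistry, Hematology" marks weeks 4, 12, 52 and 64 for all subjects. The ECG row marks weeks 4, 12 and 52. Both rows carry two conditional entries:

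- week 24, footnote c: "Only for subjects who increased IP to 140 mg at week 12, 16, or 20"
- week 36, footnote d: "Only for subjects who increased IP to 140 mg at week 24 or 28"

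Protocol 3.1 lets subjects already enrolled move from "70 mg QM to 140 mg QM at the first available opportunity at either week 4, 8, 12, 16, 20, 24, or 28 visits". Those who switch at week 4 or 8, start on 140 mg, or stay on 70 mg have no added panel or ECG.

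**Columns.** SAP 10.6 groups non-AE safety data by share of exposed time. The 70 mg and 140 mg columns each need at least 80% of that time at the dose. The third column is "70/140 mg mix: including all subjects who receive any one dose <80% of the time exposed". Read literally, that wording would catch everyone, because a subject always on 140 mg has 0% on 70 mg. SAP Appendix C describes the third group as the remaining subjects, so it is taken here as neither dose reaching 80%.

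**Tables.** SAP 10.6.2 plans a by-group shift table of the worst laboratory grade reached after the first dose in this study. It also plans "Subject incidence of liver function test abnormalities" by group. SAP 10.6.5 adds "A summary of ECG diagnoses will be tabulated" and gives no grouping or counting rule.

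**The concern.** A worst-grade table and a subject-incidence table both count a subject once if any test qualifies. An added test cannot lower either figure and can raise it. If one column is tested more often by design, part of any excess in that column comes from looking more often.

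The added panel falls 4 to 12 weeks after the dose increase (for example, a switch at week 20 is tested at week 24, and a switch at week 12 at week 24). A reader could therefore take an excess in the mix column for an effect of stepping up. Safety is the primary objective. SAP 11 expects most subjects to receive both doses, so the mix column may not be small. SAP 8 also lists laboratory and liver summaries for a possible interim analysis supporting a regulatory submission.

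The SAP deals with unequal opportunity for adverse events, using exposure-adjusted incidence with time at risk by dose level (6.6, 10.6.1.1). The laboratory incidence tables have no counterpart.

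**Working it through.** The documents give no figure on this point to reproduce.

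**Step 1: exposure of a completer.** Protocol 3.1 states "All subjects will receive open-label AMG 334 QM SC for 13 months". Table 1 has 13 doses, from day 1 to week 48 (day 337). By the SAP 6.6 formula, total duration = (337 + 27) − 1 + 1 = 364 days. For a switch at week w, the first 140 mg dose is on day 7w + 1, so the 70 mg duration is 7w days and the 140 mg duration is 364 − 7w.

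**Step 2: column and panel count.**

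| Switch week | Days at 70 mg | Days at 140 mg | Share at 140 mg | Column | Panels | ECGs |
|---|---|---|---|---|---|---|
| 4 | 28 | 336 | 92.3% | 140 mg | 4 | 3 |
| 8 | 56 | 308 | 84.6% | 140 mg | 4 | 3 |
| 12 | 84 | 280 | 76.9% | mix | 5 | 4 |
| 16 | 112 | 252 | 69.2% | mix | 5 | 4 |
| 20 | 140 | 224 | 61.5% | mix | 5 | 4 |
| 24 | 168 | 196 | 53.8% | mix | 5 | 4 |
| 28 | 196 | 168 | 46.2% | mix | 5 | 4 |

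Subjects on one dose throughout have 4 panels and 3 ECGs. Moving the switch date and the total by up to 4 days either way (the visit window) changes no classification. Among completers, the mix column and the subjects named in footnotes c and d are the same people.

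**Step 3: limit of the match.** It is exact for completers only. A week 4 switcher who stops after 3 doses of 140 mg has 84/112 = 75% at that dose and is in the mix column with no added panel. So is a week 8 switcher who stops after 7 (196/252 = 77.8%). A week 16 switcher who stops after one 140 mg dose has 112/140 = 80% at 70 mg and is in the 70 mg column.

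**Step 4: effect of one more test.** The documents give neither a per-test rate p nor a within-subject correlation, so both are assumed. With independent tests, the chance of at least one qualifying result in n tests is 1 − (1 − p)^n.

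| p | 4 panels | 5 panels | Ratio | 3 ECGs | 4 ECGs | Ratio |
|---|---|---|---|---|---|---|
| 1% | 3.94% | 4.90% | 1.24 | 2.97% | 3.94% | 1.33 |
| 2% | 7.76% | 9.61% | 1.24 | 5.88% | 7.76% | 1.32 |
| 5% | 18.55% | 22.62% | 1.22 | 14.26% | 18.55% | 1.30 |

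If a subject's results are fully correlated, the added test finds nothing new and every ratio is 1.0.

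**The case against.** **A common-visit filter in place of the planned tables would do harm.** This is the strongest point, and it stands. Dosing is the last procedure of a visit (Protocol 6.2.1.1), so a test at the switch visit precedes the higher dose. Counting tests after the first 140 mg dose and up to week 52, week 4 and 8 switchers have weeks 12 and 52, week 12 to 20 switchers have weeks 24 and 52, and week 24 and 28 switchers have weeks 36 and 52. The footnotes thus give every completing switcher two. A filter leaves week 12 to 28 switchers with week 52 alone. It could also drop early-termination samples, which SAP 6.4 maps by study day, and unscheduled results such as the repeat liver tests in Protocol Appendix A. The filtered table can only be a supplement.

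**The effect is a tendency.** A reader might infer that the mix column will show more abnormalities. The documents do not support that. At p = 2% the gap is 9.61 − 7.76 = 1.85 points with full independence. If the maximum of 651 subjects split evenly between two columns, the standard error of the difference would be about √[(0.0961 × 0.9039 + 0.0776 × 0.9224)/325] = 2.2 points. The mix column would then be the higher one in roughly 80% of such trials. The real column sizes are not given.

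**ECG.** A reader might extend the point to ECG diagnoses. SAP 10.6.5 disclaims summaries of ECG measurements and gives no grouping or any-occurrence rule for diagnoses, and SAP 14 lists ECG data as not covered. Only the general wording of SAP 10.6 on other non-AE safety data suggests the three columns. The ECG ratios are therefore conditional.

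**No between-group testing is planned.** This is true, and the by-visit summaries of ANC, ALT and AST change are unaffected. But the columns are printed side by side and will be compared by eye, so the lack of a test does not remove the imbalance.

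**Everyone already gives blood at week 24.** This is also true: PK and antibody samples are taken then. What is unequal is the chemistry/haematology panel.

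**Conclusion.** The point holds for the laboratory tables. Completers in the mix column have 5 scheduled post-baseline panels against 4 elsewhere, and SAP 10.6.2 plans worst-grade and any-occurrence tables by those columns with no allowance for the difference. With no dose effect, the mix column tends to be higher, by a ratio between 1.0 and about 1.24. That range rests on an assumed 1% to 5% rate per test and on within-subject correlation running from complete to none. It applies to completers; early stoppers, or subjects cut off at an interim analysis, can be classified differently.

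For ECG diagnoses (4 against 3), the same would follow only if they are counted as any occurrence in these columns, which the SAP does not say. The added tests themselves are not an error, since they supply the switchers' first scheduled panel on the higher dose. The imbalance is modest and descriptive, and worth a cheap improvement to the SAP.

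**What to change.** 1. Keep the SAP 10.6.2 by-group tables on all samples, including week 24 and 36, early-termination and unscheduled results.
2. Add a companion by-group table of worst-grade shift and liver-abnormality incidence, restricted to the scheduled visits common to all subjects: weeks 4, 12, 52/ET and 64. Count early-termination samples by nominal visit so that the study-day windows do not remove them.
3. Report the number of tests per subject in each column, and state that any reading between columns rests on the companion table.
4. In SAP 10.6.5, state the grouping and counting rule for ECG diagnoses. If they are tabulated by group, add the same companion on weeks 4, 12 and 52/ET.

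The cost is SAP wording, a visit filter and one extra table (a second if ECG diagnoses are grouped). No data collection changes and no safety result is lost. The companion table holds fewer on-140 mg tests for the week 12 to 28 switchers, and a footnote should say so.
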